Title: Evaluating values-based motivational interviewing to increase treatment completion with fixed dose combination MK-5172/MK-8742 among Veterans with active substance use disorders and treatment-naïve genotype 1 chronic hepatitis C

Investigators: [name] [name]., [name].,

1. Objective and hypotheses.

Primary Objective: Implement a values-based motivational interviewing (VBMI) intervention to promote treatment completion with fixed dose combination (FDC) MK-5172/MK-8742 (elbasvir/grazoprevir, Zepatier™) x 12 weeks among treatment-naïve Veterans with substance use disorder (SUD) and genotype 1 chronic hepatitis C virus (HCV) infection.

Primary Hypothesis: Veterans with SUD and genotype 1 chronic HCV infection who receive the VBMI intervention will complete the full course of treatment in 90% of cases.

Secondary Objectives:

- 1) Utilize VBMI to promote self-efficacy in taking FDC MK-5172/MK-8742 (elbasvir/grazoprevir, Zepatier™) among Veterans with active SUD and chronic HCV infection.
- 2) Demonstrate the feasibility of FDC MK-5172/MK-8742 (elbasvir/grazoprevir, Zepatier™) for obtaining sustained virologic response (SVR) in treatment-naïve genotype 1 chronic HCV infection among Veterans with active SUD.
- 3) Measure the prevalence of baseline NS5a resistance mutations in Veterans with active SUD and genotype 1a chronic HCV infection. NS5a is a nonstructural HCV protein.

Secondary Hypotheses:

- 1) Veterans with SUD enrolled in this study will demonstrate a trend towards clinically significant increases in HCV treatment adherence self-efficacy scores between baseline and week 4 of treatment.
- 2) FDC MK-5172/MK-8742 (elbasvir/grazoprevir, Zepatier™) will be well-tolerated by Veterans with SUD.

2. Study procedures

2.1 Background: The advent of direct acting antivirals (DAAs) for chronic HCV infection has increased the tolerability and effectiveness of curative HCV treatment. Disorders which can affect adherence to HCV treatment, including SUD, can reduce effectiveness of DAAs. During the pegylated interferon era, the VA HCV 001 study group demonstrated an association

between recent alcohol use and early treatment discontinuation, resulting in decreased treatment efficacy¹. The authors concluded that patients with alcohol use should be provided additional support to assist with treatment completion.

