2.5.1 Participant Recruitment and Enrollment: Veterans with active SUD are regularly screened for chronic HCV infection. All patients with chronic HCV are subsequently referred to the HCV treatment clinic for treatment evaluation. When evaluating a patient for HCV treatment, current diagnoses including SUD (ICD10 CM F10-F19) are routinely noted. It is standard of care for patients who are infected with HCV genotype 1a to undergo baseline resistance testing before initiation with MK-5172/MK-8742 (elbasvir/grazoprevir, Zepatier™). Patients meeting inclusion criteria will be offered study participation at their clinic visit. Basic demographic data (age-if less than 89 years, race, gender) will be recorded on all patients who are asked to participate in the study to allow investigators to assess for enrollment bias. Patients who agree to participate will give their written informed consent. Patients will be assigned a unique study number that does not contain personal identifiers after signing informed consent. Each patient will have only one number for the duration of the study. Study records will be labeled with this unique study number and will not contain PHI. Treatment will be prescribed in accordance with US labeling as described in the package insert.

Genotype 1b: 12 weeks MK-5172/MK-8742 (elbasvir/grazoprevir, Zepatier™)
Genotype 1a without NS5a RAVs: 12 weeks MK-5172/MK-8742 (elbasvir/grazoprevir, Zepatier™)
Genotype 1a with NS5a RAVs: 16 weeks MK-5172-MK-8742 (elbasvir/grazoprevir, Zepatier™) with weight based ribavirin

2.5.2 Baseline visit: Patients will complete a survey of demographic (age, gender, race/ethnicity, income level, marital status, education level, distance from medical center) and medical information. Drug Abuse Screening Test (DAST) and AUDIT will be completed to assess severity of SUD. We will also assess health related quality of life (Rand-36 item Health Survey [Short Form-36]), social support (Medical Outcomes Study Social Support Survey [MOS-SSS]), depressive symptoms (Patient Health Questionnaire [PHQ-9]), and treatment adherence self-efficacy (HCV Treatment Self Efficacy-A [HCV TSE-A]).

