2.5.3. Description of the VBMI intervention

Patients enrolled will receive 60-minute sessions at Weeks 0 and 2 and four 15-minute sessions at Weeks 4, 6, 8, and 10. The sessions at Weeks 0 and 2 will focus on identifying values and creating short-term goals within those values, consistent with an ACT framework⁶. Specifically, during these first two sessions values directly (e.g., “My health is important to me.”) and indirectly (e.g., “My family is important to me, and I need to be healthy to have time for my family.”) related to health behaviors and medication adherence will be elicited. Veterans will discuss how well they are living in accordance with their stated values and identify specific goals and objectives for increasing valued living through the use of goal-setting exercises. The sessions in Weeks 4, 6, 8, and 10 will predominately be brief “check-in” meetings that will focus on helping the participant problem solve barriers to moving towards their values. For a more comprehensive description of the intervention, see Appendix F. The therapeutic approach of all sessions will be founded in MI techniques and specifically utilize the four core processes of *engaging* the Veteran to establish rapport, *focusing* the conversation on unhealthy behaviors and/or targets for change, *evoking* change-oriented talk and increased self-confidence, and *planning* specific practical steps for making change. All sessions will be conducted by a licensed psychologist who has extensive knowledge in ACT and MI or by a trained post-doctoral fellow under the supervision of a licensed psychologist. The sessions will be recorded (audio only) for the purposes of monitoring adherence of the psychologist to the VBMI protocol.

2.5.4 Description of instruments:

The **Rand-36 item Health Survey (SF-36)** is a validated instrument which evaluates physical and mental health. The 36 questions cover 8 domains: physical function, role function as limited by physical health, bodily pain, social functioning, mental health, role function as limited by emotional health, vitality and general health perception. The survey was developed by Rand Corporation as part of the Medical Outcomes Study and has been previously used in Veterans with hepatitis C.

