The **Medical Outcomes Study Social Support Survey (MOS-SSS)** has also been widely used and validated among persons with chronic medical illness, including Veterans with chronic hepatitis C. This 19-item survey assesses the patients’ perceptions of their existing emotional support, tangible support, affectionate support, and social interactions.

The **Patient Health Questionnaire (PHQ-9)** is a validated survey of depressive symptoms. Higher scores indicate a greater likelihood of clinical depression. This survey is currently used to screen for depression annually in Veterans in care at VA Medical Centers.

The HCV-Treatment Self Efficacy (HCV-TSE) is a standardized survey which assesses self-belief that a patient can complete his/her treatment regimen of pegylated interferon and ribavirin. The patient rates their confidence in their ability to take medications on a scale of 0 to 10, where 0 indicates no confidence and 10 indicates full confidence. The answers to the four individual questions are averaged to a score of 0 to 10. We have adapted 4 questions from the original scale regarding medication adherence (**HCV-TSE-A**) to assess a patient's perceptions of his/her ability to adhere to DAAs.

2.5.5 Follow-up visits:

The study will last 12 weeks, with follow up visits at Weeks 2, 4, 6, 8, 10 and 12, which will be coordinated to occur on the same date as Veterans' substance abuse aftercare visits. Side effects of medications and tolerance of medications will be monitored at each visit using a single question about side effects experienced and response options including the most common side effects and a response of "other" and a description of that side effect. A single question will also be used to assess for any substance use since the last visit, with quantity and frequency being recorded if the response is positive.

Adherence will be assessed at each follow up visit using the Visual Analog Scale and pill counts. Routine laboratory monitoring will include a CBC, CHEM 14, HCV RNA and a urine sample analyzed for cocaine, marijuana, opioid, and amphetamine use (all tests are standard of care). The HCV-TSE-A will be repeated at week 4. Assessments of depressive symptoms (PHQ-9) and health-related quality of life (SF-36) will be repeated at weeks 4 and 12.

If a patient fails to complete the study, a lost to follow up form will be completed,

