Patients will be assigned a unique study number which does not contain PHI. This number will be used on all data collected for the purposes of this study. A master list of subjects which links the study number and patient identifiers will be maintained on an encrypted VA server. The data for this study will be entered into Microsoft Excel 2010. The investigator(s) and their research personnel are responsible for maintaining the study database, which will be kept on an encrypted VA server. No data will be stored on a hard drive of a PC. Only key personnel for this study will have access to the research data and access to this data will be terminated if/when the personnel are removed from the study. Research data will be maintained according to the VA records schedule. Data containing PHI will not leave the VA premises. A contract biostatistician will be used to analyze de-identified study data.

Variables/Time Points of Interest

The primary outcome of interest is the percentage of patients completing 12 weeks of treatment with FDC MK-5172/MK-8742 (elbasvir/grazoprevir, Zepatier™). Treatment completion will be defined as attendance at the last treatment visit (i.e., Week 12). Adherence will be categorized into <90% adherence and ≥ 90% adherence, based on an observed relationship between ribavirin adherence and early virologic response¹¹.

Statistical Methods

Binary logistic regression analysis will be used to report adjusted odds ratios. Differences in the distribution of HSV-TSE-A scores across categorical visits (baseline vs. Week 4) will be assessed using Wilcoxon rank sum test. In addition, parametric models (linear regression) will be explored to estimate the differences.

Power/Sample Size:

In our pilot program of 4 Veterans, we found that 75% completed 12 weeks of treatment. Estimating a 90% (18/20) completion rate in the VBMI arm, we anticipate that a sample size of 20 patients will demonstrate a trend towards higher completion rates with the VBMI intervention. We also anticipate the study will demonstrate a high rate of medication adherence. It is our intention to use data from this study to develop larger protocols with more robust sample sizes.

Limitations:

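### The baseline-to-Week 4 self-efficacy comparison is paired, but the only test named for it, the Wilcoxon rank sum test, is for two independent samples

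*Combined protocol and SAP*

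**What the plan says.** Secondary Hypothesis 1 (section 1) is that enrolled Veterans "will demonstrate a trend towards clinically significant increases in HCV treatment adherence self-efficacy scores between baseline and week 4 of treatment". The scale is completed at the baseline visit (section 2.5.2), and section 2.5.5 adds: "The HCV-TSE-A will be repeated at week 4". It is the average of four items, on a 0 to 10 scale (section 2.5.4).

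Section 2.2 describes one group of 20 Veterans. Section 2.5.3 gives the intervention to everyone: "Patients enrolled will receive 60-minute sessions at Weeks 0 and 2". There is no comparison group. Section 2.5.1 makes the two scores linkable: "Each patient will have only one number for the duration of the study".

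The Statistical Methods section names the test: "Differences in the distribution of HSV-TSE-A scores across categorical visits (baseline vs. Week 4) will be assessed using Wilcoxon rank sum test". (HSV-TSE-A is evidently a typing error for HCV-TSE-A.) It then says that "parametric models (linear regression) will be explored to estimate the differences". The document mentions no signed-rank test, paired test, change score, mixed model or patient effect.

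**The concern.** The rank sum test is built for two independent samples. Here the two samples are the same people measured twice. If a Veteran who scores high at baseline also tends to score high at Week 4, the stable differences between Veterans cancel out of each one's change. The rank sum test still counts those differences as noise, so its standard error is too large and its p-value too high. A real gain is then more likely to be missed.

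A linear regression of score on visit has the same fault unless the within-patient correlation is modelled, and the plan does not say that it will be.

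This is the only test named for Secondary Hypothesis 1, and the sample is small. The Power/Sample Size section intends the data to support larger protocols. An unpaired analysis does not give the SD of within-patient change, which is what sizing a later paired comparison would need.

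**Working it through.** **No plan figure to reproduce.** The only sample-size arithmetic (18/20 = 90%, against a pilot rate of 3/4 = 75%) concerns treatment completion. No power, SD, effect size or significance level is given for the self-efficacy comparison.

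**Inputs from the plan**
- At most 20 pairs (section 2.2; Power/Sample Size).
- Same patients at baseline and Week 4 (sections 2.5.2 and 2.5.5).
- Score range 0 to 10 (section 2.5.4).

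**Inputs assumed**
- Two-sided 5% level.
- Within-patient correlation ρ from −0.3 to 0.8.
- True gain d of 0.3, 0.5 or 0.8, in units of the SD σ of a single score.
- Equal SDs at the two visits, and no missing Week 4 scores except where stated.

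**Step 1: what ignoring the pairing does.** The unpaired analysis takes the variance of the mean difference as 2σ²/n. The true variance is 2σ²(1 − ρ)/n. The standard error is therefore overstated by a factor 1/√(1 − ρ), which is 1.20, 1.41 and 1.83 at ρ = 0.3, 0.5 and 0.7.

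**Step 2: normal approximation.** These formulas are for means, and serve as a check on the rank tests.
- Actual type I error of the unpaired test: 2[1 − Φ(1.96/√(1 − ρ))]. At ρ = 0.3, 0.5 and 0.7 this is 2[1 − Φ(2.34)] = 1.9%, 2[1 − Φ(2.77)] = 0.6% and 2[1 − Φ(3.58)] = 0.03%.
- Power of the paired test: Φ(d√n/√(2(1 − ρ)) − 1.96). With d = 0.5, n = 20 and ρ = 0.5 this is Φ(2.236 − 1.96) = 61%. It is 47% at ρ = 0.3 and 82% at ρ = 0.7.
- Power of the unpaired test: Φ((d/√(2/n) − 1.96)/√(1 − ρ)). With the same values at ρ = 0.5 this is Φ((1.581 − 1.96)/0.707) = 30%. It is 32% at ρ = 0.3 and 24% at ρ = 0.7.

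**Step 3: simulation of the two rank tests.** 10,000 replicates per setting, bivariate normal scores, 20 pairs. Each cell gives rank sum / signed-rank.

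| ρ | Type I error | Power, 0.3 SD | Power, 0.5 SD | Power, 0.8 SD |
|---|---|---|---|---|
| −0.3 | 8.0% / 4.7% | 17.6% / 12.0% | 34.0% / 25.1% | 64.9% / 54.0% |
| 0 | 5.1% / 4.9% | 14.4% / 14.2% | 31.7% / 30.5% | 66.5% / 64.6% |
| 0.3 | 2.3% / 5.1% | 10.4% / 17.7% | 29.2% / 41.0% | 69.9% / 80.4% |
| 0.5 | 0.9% / 5.0% | 7.8% / 23.7% | 27.6% / 54.9% | 72.6% / 91.1% |
| 0.7 | 0.2% / 5.0% | 4.4% / 35.9% | 23.3% / 76.1% | 77.4% / 99.1% |
| 0.8 | <0.1% / 4.8% | 2.8% / 49.4% | 22.0% / 90.4% | 81.1% / 99.9% |

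For a 0.5 SD gain the loss is 41.0 − 29.2 = 11.8 points at ρ = 0.3, 54.9 − 27.6 = 27.3 at 0.5 and 76.1 − 23.3 = 52.8 at 0.7. The apparent advantage of the rank sum test at ρ = −0.3 comes with an inflated type I error.

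**Step 4: sensitivity, 0.5 SD gain**
- 16 complete pairs: 19.2% against 42.3% at ρ = 0.5, and 16.2% against 64.6% at ρ = 0.7.
- Score in steps of 0.25 and capped at 10 (assumed mean 8, SD 1.5; 1,500 replicates): 27.0% against 38.6%, 25.3% against 52.3% and 21.9% against 71.9% at ρ = 0.3, 0.5 and 0.7. The pattern is the same.

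**The case against.** The strongest reply is about proportion. This is a secondary hypothesis, worded as a trend, in a 20-patient pilot, and no significance level is stated for it. With positive correlation the error is conservative and creates no false claim of benefit. Nothing is irrecoverable, because the paired test can be run later on the same data. All of that is true, and it limits the consequences. It does not make the named test suit the design. A small sample is where the pairing is most worth keeping, and switching tests after seeing the data would look selective.

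The power loss also depends on a correlation that the documents do not give. A separate run of 3,000 replicates at 0.5 SD gave 32% against 34% at correlation 0.1 and 31% against 37% at 0.2. For a 1.0 SD gain it gave 88% against 94% at correlation 0.3 and 92% against 99% at 0.5. Low correlation cannot be excluded, since the four items were adapted by the investigators, no repeatability figure is given, and two 60-minute sessions precede Week 4. So the size is conditional, and a large gain would probably be detected either way.

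Three smaller points stand:
- The plan promises no confidence interval here, so the excess width applies only if one is taken from the unpaired analysis.
- The form of the regression is not given. A regression of change scores, or of Week 4 on baseline, would be valid, so the firm criticism there is under-specification.
- A signed-rank test needs rules for missing Week 4 scores and for zero changes.

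Rank sum may simply be a slip for signed-rank. The text nevertheless treats the visits as categories, and the contract biostatistician may run it as written.

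**Conclusion.** The concern holds: the test is wrong as written. That follows from the design and the named test alone and needs no assumption. The p-value is invalid unless baseline and Week 4 scores are uncorrelated. It is too large under positive correlation, the usual case for repeat scores in one person, and too small under negative correlation.

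The size does rest on assumptions: correlation, effect size, a two-sided 5% level and roughly normal scores. For correlations of 0.3 to 0.7 and a 0.5 SD gain, the planned test gives up about 12 to 53 points of power and runs at a type I error of 2.3% down to 0.2%. The loss shrinks to nothing at zero correlation, and it is smaller in points for large gains. The effect is confined to Secondary Hypothesis 1.

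**What to change.** In Statistical Methods, replace the rank sum sentence with wording such as:

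> The change in HCV-TSE-A from baseline to Week 4 will be tested with the Wilcoxon signed-rank test on each Veteran's Week 4 minus baseline score. The median change and its 95% confidence interval will be reported.

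Replace the unspecified linear regression with a paired analysis of change or a mixed model with visit as a fixed effect and a random patient effect.

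In the same edit:
- state the significance level and sidedness;
- say how a missing Week 4 score is handled (for example, complete pairs, with the number and reasons for missing scores reported) and how zero changes and ties are treated;
- report the SD of within-patient change and the baseline-to-Week 4 correlation, for planning later studies;
- correct HSV-TSE-A to HCV-TSE-A.

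The core change costs about one line and the additions a few more. No new data, visits or patients are needed, because the study number already links the two scores. The edit should be made before the data are analysed.

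### A single group of 20, all given VBMI, cannot show higher completion than a 3-of-4 pilot; *trend* has no cut-off, and no interval is planned for the primary percentage

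*Combined protocol and SAP*

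**What the plan says.** **Outcome and hypothesis.** Section 1 hypothesises that 90% of Veterans given VBMI will complete treatment. Under Variables/Time Points of Interest, "The primary outcome of interest is the percentage of patients completing 12 weeks of treatment", with completion counted as attendance at the Week 12 visit.

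**Sample size.** Power/Sample Size gives the pilot rate as 75% of 4 Veterans. It continues "Estimating a 90% (18/20) completion rate in the VBMI arm" and concludes "we anticipate that a sample size of 20 patients will demonstrate a trend towards higher completion rates with the VBMI intervention". It states no alpha, sidedness, power, test or threshold. It closes: "It is our intention to use data from this study to develop larger protocols with more robust sample sizes".

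**Design.** Section 2.2 describes one prospective group of 20. Section 2.5.3 says "Patients enrolled will receive 60-minute sessions at Weeks 0 and 2", followed by four shorter sessions. No group without VBMI is described.

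**Reference.** Section 2.3.1 reports four Veterans who started HCV treatment during residential SUD treatment. Three finished 12 weeks and one was lost to follow-up. The study itself admits residential patients and/or Veterans with a SUD diagnosis code in the previous 6 months.

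**Analysis.** Statistical Methods says "Binary logistic regression analysis will be used to report adjusted odds ratios", with no outcome, exposure or covariates named. The sentence just before that section begins "Adherence will be categorized into <90% adherence" and sets the other category at 90% or above. The remaining methods, a rank-sum test and linear regression, are for the self-efficacy scores.

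**The concern.** A claim of higher completion with an intervention needs something to compare with. Here exposure does not vary within the study, and the outside reference is four patients. Those four were all in residential treatment, whereas the study also takes Veterans on a diagnosis code. Their result is described as finishing 12 weeks of treatment, whereas the study counts attendance at a visit. A higher rate could reflect the population, the definition, chance or VBMI, and the design cannot separate them.

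The analysis does not repair this. The primary outcome is a single percentage, but no interval is stated for it, and the only method named for a binary outcome reports adjusted odds ratios.

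The results are meant to inform larger protocols. If the plan is followed as written, a later trial could inherit an effect attributed to VBMI that was never estimated, and a completion rate without its uncertainty.

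**Working it through.** **Inputs.** N = 20, anticipated 18/20 and pilot 75% of 4 (Power/Sample Size); pilot count 3 of 4 (Section 2.3.1); hypothesised rate 90% (Section 1).

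**Step 1: the plan's own figures.** 18/20 = 90% and 3/4 = 75%; both reproduce. N = 20 cannot be reproduced as a power calculation because the plan states no alpha, power or test.

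**Step 2: precision.** The exact (Clopper-Pearson) 95% limits for x of n are the 2.5% quantile of Beta(x, n − x + 1) and the 97.5% quantile of Beta(x + 1, n − x).
- 18/20: Beta(18, 3) and Beta(19, 2) give 68.3% to 98.8%. The Wilson interval is 69.9% to 97.2%. Both include 75%.
- 3/4: Beta(3, 2) and Beta(4, 1) give 19.4% to 99.4%.

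The pilot is also compatible with a rate that was already 90%: P(3 or fewer of 4 | 0.90) = 1 − 0.9⁴ = 1 − 0.656 = 0.344.

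**Step 3: what *trend* could mean.** The text gives no cut-off, so three are shown. For X ~ Binomial(20, p), the chance of meeting a cut-off r is P(X ≥ r), with 75% treated as a known benchmark (an assumption). For r = 18:
- p = 0.75: 190(0.75¹⁸)(0.25²) + 20(0.75¹⁹)(0.25) + 0.75²⁰ = 0.0669 + 0.0211 + 0.0032 = 0.091
- p = 0.90: 190(0.90¹⁸)(0.10²) + 20(0.90¹⁹)(0.10) + 0.90²⁰ = 0.2852 + 0.2702 + 0.1216 = 0.677

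The other rows use the same sum.

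| Cut-off | True rate 75% | True rate 90% |
|---|---|---|
| 16 or more (any observed rate above 75%) | 41% | 96% |
| 17 or more | 23% | 87% |
| 18 or more (the count the text names) | 9% | 68% |

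A lenient cut-off is met often when nothing has changed. The named count is met less often by chance, but is missed about one time in three (1 − 0.677 = 0.323) when the true rate is 90%.

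**Step 4: the logistic model.** VBMI is a constant in these data, so no VBMI odds ratio can be estimated. If the model is meant for completion, the expected non-completers are 20 × (1 − 0.90) = 2, or 20 × (1 − 0.75) = 5 at the pilot rate. Two events cannot support an adjusted model.

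**The case against.** The strongest reply is that this is a pilot. It claims no significance, alpha or power, says that larger studies will follow, and any reader given x/20 can compute an interval. Much of that stands, and it limits the point in several ways.

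- A reader might infer that N = 20 is wrong or underpowered. The documents do not support that: no power is claimed, and 20 patients can give a proportion with its interval.
- A reader might infer that the plan assigns logistic regression to the primary outcome. It does not say so. The model may be meant for adherence of at least 90%, defined just before it. The fault is that its outcome is unstated and that no interval is given for completion.
- A reader might take 41% as the plan's false-positive rate. The cut-off of 16 is supplied here. At the 18/20 that the text names, the figure is 9%.
- A reader might infer that no result could separate the study from 75%. At 19/20 the exact lower limit is 75.1%. That would exclude only a fixed 75%, not the pilot's own uncertainty, and would still not attribute the difference to VBMI.
- A reader might infer that all enrolled Veterans must be the denominator. Section 2.5.1 says "Patients will be assigned a unique study number that does not contain personal identifiers after signing informed consent", which would allow it. But the primary hypothesis concerns Veterans who receive VBMI, and the pilot counted those who started treatment. The documents do not settle the choice.

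The reply does not rescue the comparative sentence. Pilot status makes the interval more useful, and Limitations mentions neither the absent control nor the four-patient benchmark.

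**Conclusion.** The point holds, and should be fixed. The plan states that the study will show higher completion with VBMI, and a single group set beside 3 of 4 patients cannot show that. At the anticipated 18/20 the exact 95% interval runs from 68.3% to 98.8% and includes 75%; the pilot's runs from 19.4% to 99.4%. Depending on the cut-off, a *trend* would appear in 9% to 41% of studies at a true 75%, and in 68% to 96% at a true 90%.

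Those chances treat 75% as known and as the rate without VBMI. Section 2.3.1 implies the latter but does not say what support the pilot patients received. The intervals and the lack of a control do not depend on these assumptions. The sample size itself is not at fault.

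**What to change.** - Make the primary analysis the completion proportion with an exact (or Wilson) 95% CI.
- Replace the trend sentence with: *20 patients; if 18 complete, 90% with exact 95% CI 68–99%; not designed to show improvement over the pilot.*
- Delete *arm*.
- Do not report adjusted odds ratios for completion.
- For adherence of at least 90%, report the proportion with its CI. The plan also anticipates a high adherence rate, so events may again be few and naming covariates would not cure that. Treat any logistic model as exploratory, fitted only if events allow, with its outcome and covariates stated.
- State the denominator for completion. No particular choice is urged here.

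The cost is wording in the sample-size and analysis text, with no extra patients, visits or data. The downside is a more modest claim: the study would no longer state that VBMI raises completion.
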